SCION NEUROSTIM, LLC:

Title: A Non-Invasive Neuromodulation Device for Prevention of Episodic Migraine Headache

Background

This study is a multi-center, triple-blinded, placebo-controlled, randomized clinical trial for adjunctive prophylactic treatment of episodic migraine headache (with or without aura) using a caloric vestibular stimulation (CVS) device developed by Scion NeuroStim, LLC (SNS). The investigational use of the CVS device for episodic migraine headache has been reviewed by the FDA and is classified as NSR (non-significant risk).

Efficacy of neuromodulation therapy for migraines is reasonably well-established. Traditionally, however, neuromodulation, especially when accomplished through an expensive, surgically implanted device, has been available only as a treatment of last resort, to be used (and covered by health insurance) if, but only after, patients have failed all other interventions, principally pharmaceuticals. Typically, patients receive neuromodulation for migraines only after they are refractory or close to being refractory. SNS envisions changing that paradigm, providing effective early interventions and thereby improving outcomes for migraine patients. The CVS device is non-invasive and utilizes the same underlying mode of neural modulation (activation of the vestibular nuclei in the brainstem) that for a century has been well-understood by the medical profession and has been used safely via caloric irrigators for diagnostic purposes, for example in ENT practices to assess balance and in the ED to assess brain function. The device is easy to operate; it can be used safely at home by a patient under the supervision of a prescribing physician. Through availability and use of the CVS device, prophylactic neuromodulation therapy for migraines can become an inexpensive and early, rather than an expensive and belated, therapeutic option.

A pivotal RCT study of episodic migraine headache using the device has been completed (NCT01899040). The primary endpoint was met. Active arm subjects showed immediate and steady declines in migraine days over the treatment period and exhibited significantly fewer migraines during the third treatment month (-3.6 ± 0.7 days, $-46.1\% \pm 7.3\%$), than placebo arm subjects (-0.9 ± 0.7 days, $13.5\% \pm -14.1\%$, $p = 0.014$). The study described herein is designed to further the evaluation of CVS neuromodulation, addressing the following aims:

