The design size contemplates enrolling up to one hundred and twenty (120) subjects who will successfully follow through to completion of their participation in at least the first treatment portion of the study (first 3-month treatment period). The subjects will be randomly assigned to: twice-per-day active, once-per-day active or twice-per-day placebo in a 1:1:1 ratio.

The results of the first migraine RCT did not show evidence of stratification based on gender or clinical site or baseline headache frequency. Envelopes containing

randomization assignments will be grouped in batches of six, each batch containing two of each of the three assignment arms. The batches of envelopes will be randomly shuffled by an agent not involved with the study. A given batch will be completed before the next batch is opened. This procedure results in 20 possible different arrangements, for six subjects, of the ordering of treatment and placebo assignments. The unblinded coordinator will record the subject's designation but will not share the assignment with the subject, principal investigator, or statistician. Each study site will be individually randomized (no central randomization).

The assessment of the primary endpoint will be completed by a blinded, central statistician. The subjects will be told, within the informed consent document, of the existence of a placebo arm. Subjects will be told that the device stimulates the brain stem. Subjects will be told that they will receive at least 3-months of active treatment during the 6-month treatment period. In fact, subjects in the placebo arm in the first 3-month period will be switched to active in the second 3-month period. Subjects will be asked to guess (and provide reasons) about their treatment assignment at the end of the first 3-month treatment period and at the end of the second 3-month treatment period. Subjects will also be asked, after their very first treatment in the clinic, a series of questions designed to assess the quality of blinding (to provide evidence that the placebo device is an effective sham).

4) Study Schedule; Subject Enrollment and Activities

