The study period will last 280 days (plus additional visit window days, as needed), beginning with a pre-treatment baseline period of one month (28 days), at the end of which the principal investigator will reconfirm the appropriateness of the subject's participation in the study, followed by a first treatment period of three months (84 days), followed by a second treatment period of three months (84 days), followed by a post-treatment diary period of three months (84 days).

As noted, subjects will be advised that during the study period they may maintain patterns of usage of approved therapeutic medications that they normally use and that they should not initiate new medications, medicating patterns or other interventions. Accommodations for rescue medications will be made.

The study will be segmented with the following aims:

1. Baseline period and the first 3-month treatment period: **This portion of the study will be viewed as a complete RCT in-and-of itself and will be analyzed while the remainder of the study is still underway. The primary endpoint applies to this portion of the study.** Subjects will use an electronic data capture system that records headache pain level, duration and associated symptoms, acute medication use, and whether the headache was a migraine headache. Also, subjects will record any occurrence of an adverse event (AE).
2. Months 5-7 (from the start of the baseline period): All subjects will be assigned to the active device. Subjects will treat with the same frequency as they did in the first 3-month treatment period (e.g., BID in the first period means BID in the second period). Subjects will record the occurrence of a headache and whether

the headache was a migraine headache. Subjects will report any adverse events to the unblinded site coordinator.

3. Months 8-10 (from the start of the baseline period): Subjects will no longer be treating with the CVS device. Subjects will record the occurrence of a headache and whether the headache was a migraine headache. Subjects will report any adverse events to the unblinded site coordinator.

The phases and activities of the study are listed below:

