- (iii) Also, women of childbearing age will complete a urine-based pregnancy test to reconfirm that they are not pregnant. The unblinded coordinator will open, at random, an envelope assigning the subject to one of the three study arms. The clinic period is described below. During the first visit, the subject will complete a training session based on a set training module. The subject will complete a proficiency evaluation and the study coordinator will certify the subject's proficiency in the use of the CVS device. The study coordinator will

complete a visit assessment form. At the end of training, a first usability questionnaire will be completed by the subject.

(iv) **First Treatment Period:** The eighty-four days (3 months) following the pre-treatment baseline period constitute the first treatment period. This is the test period, the results from which will be measured against the pre-treatment baseline period data in assessing the study endpoints. Specifically, data from the last month of the first treatment period will be compared with the one-month-long pre-treatment baseline period. As close as possible (as scheduling permits) to two weeks after the start of treatment, a clinical visit will occur and another visit assessment form will be completed. A second usability questionnaire will be completed. The subject will be asked to bring the CVS device to the clinic to perform a treatment in front of the unblinded study coordinator to reaffirm proficiency in using the device. Any issues related to balance or other safety concerns will promptly be referred to the site principal investigator, who can terminate the subject's further participation in the study if necessary.

(v) **End of First Treatment Period – Start of Second Treatment Period:** At the end of the first treatment period the subject will be asked to return to the clinic and will be asked to complete the QOL questionnaires and a third usability questionnaire. All subjects will receive new SD cards for the second treatment period and the old SD cards will be retained so that treatment compliance logs can be extracted. All subjects will receive active treatment cards with the following assignments (first treatment period -> second treatment period):

- BID placebo -> BID active
- BID active -> BID active
- QD active -> QD active

Subjects will perform a treatment in front of the unblinded coordinator to re- confirm their ability to properly use the device.

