- To assess whether BID active treatment provides therapeutic gains over QD active treatment, the reductions in migraine headaches, the reduction in the number of acute (prescribed) medication taken, the reduction in subject-perceived headache pain scores, the normalized percent-change in monthly headache days, and the 50% responder rates in the BID active-treatment subjects and QD active-treatment subjects during the following periods will be compared: the first treatment month, the third treatment month, the sixth treatment month and the final month of the post-treatment period. Additionally, change scores for the QOL measures (HIT-6, BDI, BAI and the Pittsburgh Sleep Quality Assessment) at the end of the first and second treatment periods and the post-treatment observation period will also be assessed. The response kinetics for each of these parameters will be evaluated by comparing time courses for each of the three treatment arms. All change scores will be calculated relative to baseline measures.
- To assess whether six months of active treatment provides improved levels of migraine prevention relative to three months of active treatment, comparisons of the reductions in migraine headache days, the reduction in the number of acute (prescribed) medication taken, the reduction in subject-perceived headache pain scores, the normalized percent-change in monthly headache days, and the 50% responder rates during the third treatment month and the sixth treatment month (relative to baseline) for the QD active and the BID active groups will be performed. Change scores for the QOL measures (HIT-6, BDI, BAI and the Pittsburgh Sleep Quality Assessment) for the QD active and the BID active groups at the end of the first and second treatment periods (relative to baseline) will also be compared. Additionally, these measures will also be compared between the BID active and BID placebo groups during the sixth treatment month. All change scores will be calculated relative to baseline measures.

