- To assess whether CVS therapy provides durable migraine prevention after therapy has ceased, the number of migraine days, the reduction in subject-perceived headache pain scores, the number of acute (prescribed) medication taken, during each month in the post-Tx observation period will be compared to both baseline and the final treatment month in all 3 treatment groups. The normalized percent-change in monthly headache days and the 50% responder rates (relative to baseline) will also be assessed. Additionally, the QOL measurements (HIT-6, BDI, BAI and Pittsburgh Sleep Quality Assessment scores) at the final visit will be compared to both the baseline and the 6 month scores.
- Measures of body mass index for each subject will be calculated at baseline, after three and six months of treatment and after the post-treatment observation period and compared across the three treatment

arms.

- Measures of depression (Beck Depression Inventory) and anxiety (Beck Anxiety Inventory) for each subject will be calculated at baseline, after three and six months of treatment and after the post-treatment observation period and compared across the three treatment arms.
- To assess whether the reduction in migraine days relates to the number of active CVS treatments performed, correlational analyses will be performed to assess whether the change in the total number of headache days during defined study periods (first treatment period, second treatment period and post-treatment observational period) is a function of the cumulative CVS treatments performed. Additionally, approaches such as the GLIMMIX procedure for generalized linear mixed models will also be performed to determine the probability of a headache on any given day is predicted by the cumulative number of active treatments performed.

As noted above, the baseline period and the first 3-month treatment period will constitute a complete RCT. Those data will be analyzed when the targeted number of subjects (120) complete the first treatment period. Subjects will continue on to the second 3-month treatment period without interruption, as they progress through the study period. For additional clarity, the stated primary endpoint will be evaluated for the baseline period + first 3-month treatment period.

[figure not shown]
8) Statistical Analysis and Study Size

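### The daily headache model names cumulative active treatments as its only predictor; without a time term, a decline common to all arms is credited to the device

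*Combined protocol and SAP*

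**What the plan says.** The last bullet under Secondary Endpoints in section 7 plans two analyses relating benefit to the amount of treatment. The first is a correlation: whether the change in total headache days over each study period "is a function of the cumulative CVS treatments performed". The second is a daily model: "approaches such as the GLIMMIX procedure for generalized linear mixed models will also be performed", to find whether "the probability of a headache on any given day is predicted by the cumulative number of active treatments performed". The cumulative count is the only predictor named. Neither section 7 nor section 8 gives this model a term for study time, period, arm or baseline frequency, a random-effects structure, or an analysis window.

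The nearest text on time belongs to a different endpoint, the comparison of the two active frequencies: "The response kinetics for each of these parameters will be evaluated by comparing time courses for each of the three treatment arms". That is a separate analysis and not a term in the daily model.

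Three other places matter. Section 3 randomises to "twice-per-day active, once-per-day active or twice-per-day placebo in a 1:1:1 ratio". Section 4 moves the control arm in the second period ("BID placebo -> BID active"). The Background reports that in the earlier trial's third treatment month the active arm had significantly fewer migraine days "than placebo arm subjects (-0.9 ± 0.7 days").

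**The concern.** Within a treated subject, cumulative treatments and study day move almost together. If headache frequency falls over time for any reason shared by all arms, such as placebo response, a model holding only the treatment count has nowhere else to put that fall. The coefficient for the count absorbs it.

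The analysis is meant to show that benefit grows with use. A significant coefficient would be read that way, and section 8 sets a 5% Type I error without exempting secondary analyses. If the false-positive rate is far above 5% whenever there is a general decline, the result cannot support the claim.

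**Working it through.** **1. The plan's own figure.** Section 8 gives a detectable difference of 2.13 days with 40 per arm, SD 3.36, 5% alpha and 80% power. The normal approximation is (1.960 + 0.842) × 3.36 × √(2/40) = 2.10 days. The noncentral t calculation gives 2.13 days at 80.0% power. The figure reproduces. The plan gives no figure for the daily model.

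**2. How the count moves, at full adherence.**

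| Arm | Day 84 of treatment | End of second period |
|---|---|---|
| BID active | 2 × 84 = 168 | 336 |
| QD active | 84 | 168 |
| BID placebo, then BID active | 0 | 2 × 84 = 168 |

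Only the placebo arm in period 1 shows treatment time passing with no active treatment. In period 2 no arm does.

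**3. Simulation inputs.** From the documents: three arms, 40 per arm, a 28-day baseline, two 84-day treatment periods, and a fall of 0.9 days per month (the earlier trial's placebo change). Derived: a baseline of 3.6 / 0.461 = 7.8 days per 28, from the earlier trial's active-arm change of 3.6 days (46.1%). Assumed: adherence about 85%, between-subject SD 0.45 on the logit scale, a decline that starts with treatment and levels off at month 3, no dropout, no serial correlation, and no device effect in any arm.

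**4. Random-intercept logistic model.** Two-sided rejection rates, 300 runs per row (simulation standard error near 5%: √(0.05 × 0.95 / 300) = 1.3 points):

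| Window | Common fall (days) | Count only | With 28-day month indicators |
|---|---|---|---|
| Baseline + period 1 | 0 | 6% | 4% |
| | 0.45 | 18% | 6% |
| | 0.9 | 67% | 6% |
| | 1.8 | 100% | 7% |
| Baseline + both periods | 0 | 2% | 4% |
| | 0.45 | 37% | 6% |
| | 0.9 | 94% | 7% |
| | 1.8 | 100% | 7% |

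Wherever there was a common fall, every rejection by the count-only model was in the protective direction. With adherence at 60% or 100% (baseline + period 1, 0.9 days), the count-only rate is 65% or 63%.

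**5. A second set-up.** A within-subject linear probability model with cluster-robust errors (1,000 trials, 0.9-day fall) gave 48% over period 1 alone, 69% with baseline added, and 85% over both periods. Repeat simulations gave 41-49% for period 1, 71-72% with baseline, and 92% for baseline plus both periods. Across all runs at 0.45 days the range was about 14-37%.

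**6. Where the decline goes.** With baseline + period 1 and a 0.9-day fall, the mean count-only coefficient is -0.152 per 100 treatments, an odds ratio of 0.86. Mid-month-3 exposure in the BID active arm is 2 × 7 × 10 × 0.85 = 119 treatments, so the fitted change is -0.152 × 1.19 = -0.18 on the logit scale. The true common decline is -0.17. Essentially all of it is assigned to treatment. With month indicators the mean odds ratio is 0.98.

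**7. Form of the time term.** With a single linear term, two-sided error rose to 14% (through week 28, 1.8-day fall) and 16% (all 40 weeks, 0.9-day fall). Month indicators over all 40 weeks still gave 11% in 150 runs (simulation standard error 1.8 points), so finer categories are preferable there.

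**8. The companion correlation.** Over a fixed period every subject has the same elapsed time, so a common decline shifts all changes equally and creates no correlation with the count. Simulated false-positive rates were 4-8%.

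**The case against.** The strongest reply is that no model has been specified. The text names a class of methods and a question, and the phrase introducing GLIMMIX leaves the details open. Nothing forbids a time term, and the time-course comparison shows that the authors thought about time. This stands in part: a reader might infer that the plan commits to a model without time, and the documents do not say that. But open wording does not supply the term either, and the one predictor that is named is the one that misleads when used alone.

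A second reply is that the placebo arm separates dose from time. It does so in period 1, but only if time is in the model. The simulations include that arm, and the count-only model still fails.

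A third is that the decline is uncertain. This stands. The input is -0.9 ± 0.7 days; if the ± is a standard error, which is not stated, the ratio is 0.9 / 0.7 = 1.3, not clearly different from zero. It also counts migraine days, whereas the daily model concerns any headache.

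Two further inferences are tempting and unsupported. One is that regression to the mean after the 4-14 day entry screen guarantees a fall. The screen is two-sided, and section 2 reports that many subjects in the first trial were excluded for exceeding 14 headache days and worries about an unusually good baseline month, so drift could go either way. The other is that the per-period correlation shares the defect; step 8 shows that it does not.

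**Conclusion.** The concern holds for the daily model. Using the only predictor named, without a term for time, credits a common decline to the device. Under the stated assumptions and a 0.9-day common fall, the two-sided false-positive rate is about 40-50% over period 1, about 70% with baseline, and 85-94% over baseline and both periods. At half that fall it is about 14-37%, and at zero it is nominal. The direction of the error follows from how the count is built; its size depends on a decline that the documents give only imprecisely, and on a simulation without dropout or serial correlation.

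A reader might go further and conclude that the plan's efficacy result is compromised. It is not: the primary comparison of BID active with BID placebo does not use this model. The point concerns one secondary analysis and the dose-response claim that it could be used to support.

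**What to change.** State in section 7 that the daily model includes study week (or 28-day month) as a categorical fixed effect, randomised arm as a main effect, and a subject random effect, and that cumulative active treatments is tested given those terms. Name the analysis window in the same place. Prefer week over month if the window runs to week 40, and do not rely on a single linear time term over the longer windows.

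The per-period correlation needs no time adjustment. It should not be confined to within-arm comparisons or adjusted for arm, since that would discard the randomised contrast between no, once-daily and twice-daily active treatment. The part of it driven by differences in adherence may be labelled as non-randomised.

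The cost is one sentence and wider intervals for the cumulative-treatment effect. No new data are needed.
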